12.2.4.5. Exploratory Subgroup Analyses

Subgroup analyses of the primary and key secondary endpoints (as defined in the Statistical Analysis Plan) will be performed. All subgroup analyses will be conducted for the ITT population. No adjustments for multiple testing will be made.

Log-rank tests, treatment effects and the associated 95% confidence intervals for the primary and key secondary efficacy endpoints within each subgroup will be provided using the Cox proportional hazard model with treatment (AMR101 or placebo), and stratification as a factor (with the exception of the subgroup analyses of those subgroup variables related to the stratification factors, i.e., CV risk category that will not have stratification as a factor).

Subgroups including, but not limited to the following, will be explored. A complete list will be prospectively defined in the Statistical Analysis Plan.

Demographics:

- Gender,
- age (<65 yr and ≥65 yr),
- race (white and nonwhite, or any other subset with at least 10% of the total number of patients),
- geography (western vs. non-western)

Disease Parameters:

- CV risk category,
- the presence/absence of diabetes at baseline,
- renal impairment

Treatment Parameters:

- by statin intensity (statin type and regimen),
- relevant concomitant medications,

Baseline Lipid and Lipoprotein Parameters:

- LDL-C (by tertile),
- HDL-C (by tertile),
- TG (by tertile),
- TG ≥150 mg/dL,
- TG ≥200 mg/dL and TG <200 mg/dL,
- combined highest tertile for TG and lowest tertile for HDL-C,
- hs-CRP (≤3 mg/L and >3 mg/L),
- Apo B (by tertile),
- non-HDL-C (by tertile)

The consistency of the treatment effects in subgroups will be assessed for the primary and key secondary efficacy endpoints. For each subgroup variable, a Cox proportional hazard model with terms for treatment, stratification factors (with the exception of those subgroup variables related to the stratification factors, i.e., CV risk category), subgroup, and treatment-by-subgroup interaction will be performed. The main treatment effect will not be tested with this model. P-values for testing the interaction terms will be provided.

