There is a growing body of evidence, encompassing molecular, cellular, animal and human studies defining the roles for O3FAs as bioactive agents for reducing the risks of and treating CVD (Torrejon 2007). Many epidemiological studies have demonstrated inverse associations between fish intake and CV mortality, and more specifically between the intake and blood levels of O3FAs and CV mortality. For example, when comparing blood levels of O3FAs among men who had died of sudden cardiac death with controls matched for age and smoking status, it was found that participants with the highest blood levels of EPA and DHA had a 90% risk reduction for sudden cardiac death compared with those with the lowest levels (Albert 2002).

Clinical trials and experimental studies, suggest important antiatherogenic and antithrombotic effects of O3FAs. These result from wide-ranging biological effects, including benefits on lipoprotein metabolism, blood pressure, endothelial function and vascular reactivity, inflammation, platelet and fibrinolytic function, cytokine production, coagulation and oxidative stress (Mori and Woodman 2006). Evidence suggests that increased consumption of O3FAs from fish or fish-oil supplements reduces the rates of all-cause mortality, cardiac and sudden death, and possibly stroke (Wang 2006). The effect was evident in both primary-prevention (general population without a history of CVD) and secondary-prevention (patients with a history of CVD) studies with a stronger effect in secondary prevention.

The Diet and Reinfarction Trial (DART) was one of the first randomized, controlled studies to demonstrate the beneficial effects of O3FAs in secondary prevention of CHD and reported a 29% reduction in all-cause mortality over a 2-year period in 2033 male MI survivors advised to increase their intake of oily fish (200 to 400 g of fatty fish per week, which provided 500 to 800 mg/day of O3FAs) (Burr 1989). While not statistically significant, there was also a trend toward a reduction in recurrent ischemic heart disease events with increased fatty fish consumption. A post hoc analysis of patients receiving fish oil capsules (900 mg/day of EPA+DHA) in DART suggested that the protective effect was attributable to O3FAs (Burr 1994). The greatest benefit was seen in fatal MIs, and this observation led to the hypothesis that O3FAs might protect the myocardium against the adverse sequela of acute ischemic stress.

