3.10. Stratification

Participants will be assigned to treatment groups stratified by CV risk category, use of ezetimibe and by geographical region (Westernized, Eastern European, and Asia Pacific countries). There are two CV risk categories:

- CV Risk Category 1: patients with established CVD defined in the inclusion criteria. Patients with diabetes and established CVD are included in this category.
- CV Risk Category 2: patients with diabetes and at least one additional risk factor for CVD, but no established CVD.

Stratification will be recorded in the IWR at the time of enrollment. Approximately 70% of randomized patients will be in the CV Risk Category 1 and approximately 30% of randomized patients will be in the CV Risk Category 2. Enrollment with patients of a CV risk category will be stopped when the planned number of patients in that risk category is reached.

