4. STUDY POPULATION

4.1. Inclusion Criteria

Patients meeting the following criteria will be eligible to participate in the study:

1. Fasting TG levels of ≥ 200 mg/dL (2.26 mmol/L) and < 500 mg/dL (5.64 mmol/L).
2. LDL-C > 40 mg/dL (1.04 mmol/L) and ≤ 100 mg/dL (2.60 mmol/L) and on stable therapy with a statin (with or without ezetimibe) for at least 4 weeks prior to the LDL-C/TG baseline qualifying measurements for randomization
 - Stable therapy is defined as the same daily dose of the same statin for at least 28 days before the lipid qualification measurements (TG and LDL-C) and, if applicable, the same daily dose of ezetimibe for at least 28 days before the lipid qualification measurements (TG and LDL-C). Patients who have their statin therapy or use of ezetimibe initiated at Visit 1, or have their statin, statin dose and/or ezetimibe dose changed at Visit 1, will need to go through a stabilization period of at least 28 days since initiation/change and have their qualifying lipid measurements measured (TG and LDL-C) after the washout period (at Visit 1.1).
 - Statins may be administered with or without ezetimibe.

NOTE: If patients qualify at the first qualification visit (Visit 1) for TG and LDL-C, and meet all other inclusion/exclusion criteria, they may be randomized at Visit 2. If patients don't qualify at the first qualifying visit (Visit 1), a second re-qualifying visit (Visit 1.1) is allowed. For some patients, because they need to stabilize medications and/or need to washout medications, the second re-qualifying visit (Visit 1.1) will be needed after the stabilization/washout period.

3. Either having established CVD (in CV Risk Category 1) or at high risk for CVD (in CV Risk Category 2). The CV risk categories are defined as follows:

CV Risk Category 1: defined as men and women ≥ 45 years of age with one or more of the following:

- Documented coronary artery disease (CAD; one or more of the following primary criteria must be satisfied):
 - Documented multivessel CAD ($\geq 50\%$ stenosis in at least two major epicardial coronary arteries – with or without antecedent revascularization)
 - Documented prior MI
 - Hospitalization for high-risk NSTEMI-ACS (with objective evidence of ischemia: ST-segment deviation or biomarker positivity)
- Documented cerebrovascular or carotid disease (one of the following primary criteria must be satisfied):
 - Documented prior ischemic stroke

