 - Symptomatic carotid artery disease with $\geq 50\%$ carotid arterial stenosis
 - Asymptomatic carotid artery disease with $\geq 70\%$ carotid arterial stenosis per angiography or duplex ultrasound
 - History of carotid revascularization (catheter-based or surgical)
- Documented peripheral arterial disease (PAD; one or more of the following primary criteria must be satisfied):
 - ABI < 0.9 with symptoms of intermittent claudication
 - History of aorto-iliac or peripheral arterial intervention (catheter-based or surgical)

OR

CV Risk Category 2: defined as patients with:

1. Diabetes mellitus (Type 1 or Type 2) requiring treatment with medication AND
2. Men and women ≥ 50 years of age AND
3. One of the following at Visit 1 (additional risk factor for CVD):
 - Men ≥ 55 years of age or women ≥ 65 years of age;
 - Cigarette smoker or stopped smoking within 3 months before Visit 1;
 - Hypertension (blood pressure ≥ 140 mmHg systolic OR ≥ 90 mmHg diastolic) or on antihypertensive medication;
 - HDL-C ≤ 40 mg/dL for men or ≤ 50 mg/dL for women;

- Hs-CRP >3.00 mg/L (0.3 mg/dL);
- Renal dysfunction: CrCL >30 and <60 mL/min (>0.50 and <1.00 mL/sec);
- Retinopathy, defined as any of the following: non-proliferative retinopathy, preproliferative retinopathy, proliferative retinopathy, maculopathy, advanced diabetic eye disease or a history of photocoagulation;
- Micro- or macroalbuminuria. Microalbuminuria is defined as either a positive micral or other strip test (may be obtained from medical records), an albumin creatinine ratio ≥ 2.5 mg/mmol or an albumin excretion rate on timed collection ≥ 20 mg/min all on at least two successive occasions; macroalbuminuria, defined as albustix or other dipstick evidence of gross proteinuria, an albumin:creatinine ratio ≥ 25 mg/mmol or an albumin excretion rate on timed collection ≥ 200 mg/min all on at least two successive occasions;
- ABI <0.9 without symptoms of intermittent claudication (patients with ABI <0.9 with symptoms of intermittent claudication are counted under CV Risk Category 1).

Note: Patients with diabetes with CVD as defined above are eligible based on the CVD requirements and will be counted under CV Risk Category 1. Only patients with diabetes and no documented CVD as defined above need at least one additional risk factor as listed, and will be counted under CV Risk Category 2.

4. Women may be enrolled if all 3 of the following criteria are met:

- They are not pregnant;
- They are not breastfeeding;

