9.2.2. Secondary Efficacy Endpoints

The key secondary efficacy endpoint is:

- The composite of death from CV causes, nonfatal MI, coronary revascularization, unstable angina determined to be caused by myocardial ischemia by invasive/non-invasive testing and requiring emergent hospitalization, nonfatal stroke, or peripheral CVD requiring intervention, angioplasty, bypass surgery, or aneurysm repair.

Other secondary efficacy endpoints are as follows (to be tested in said order):

- The composite of total mortality, nonfatal MI, or nonfatal stroke;
- The composite of death from CV causes, nonfatal MI, coronary revascularization, unstable angina determined to be caused by myocardial ischemia by invasive/non-invasive testing and requiring emergent hospitalization, peripheral CVD requiring intervention, or cardiac arrhythmia requiring hospitalization;
- The composite of death from CV causes, nonfatal MI, coronary revascularization, or unstable angina determined to be caused by myocardial ischemia by invasive/non-invasive testing and requiring emergent hospitalization;
- The composite of death from CV causes or nonfatal MI;
- Total mortality;
- Fatal and nonfatal MI (including silent MI);
- Coronary Revascularization;
- Hospitalization for unstable angina determined to be caused by myocardial ischemia by invasive/non-invasive testing ;
- Fatal and nonfatal stroke.

For the secondary endpoints that count a single event, the first occurrence of this type of event will be counted in each patient. For secondary endpoints that are composites of two or more types of events, the first occurrence of any of the event types included in the composite will be counted in each patient.

9.2.3. Tertiary Efficacy Endpoints:

- The second, third, fourth, and fifth major CV event of the primary composite endpoint. The type of (nonfatal) events may occur in any order.
- Primary endpoint in subset of patients with diabetes mellitus;
- Primary endpoint in subset of patients with metabolic syndrome;
- New CHF, new CHF leading to hospitalization, transient ischemic attack, amputation for CVD and carotid revascularization;
- Elective coronary revascularization and emergent coronary revascularization;
- New onset diabetes;
- Fasting TG, TC, LDL-C, HDL-C, non-HDL-C, VLDL-C, apo B, hs-CRP, and hsTnT: effect of baseline and on-treatment change of biomarkers on primary and key secondary endpoints;

- CV mortality;
- Cardiac Arrhythmias requiring hospitalization;
- Cardiac Arrest;

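### The planned diabetes interaction cannot tell diabetes from CV risk category, because every non-diabetic patient has established CVD; a within-Category 1 comparison should be shown beside it

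*Combined protocol and SAP*

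**What the plan says.** The text is Amendment 1, the latest full protocol text available for this review. Amendment 2 was available only as a cover page, and no SAP text was available.

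- **Entry routes (Section 4.1).** Patients enter by one of two routes: "Either having established CVD (in CV Risk Category 1) or at high risk for CVD (in CV Risk Category 2"). The first condition for Category 2 is "Diabetes mellitus (Type 1 or Type 2) requiring treatment with medication AND".
- **Stratification (Section 3.10).** The second stratum is "CV Risk Category 2: patients with diabetes and at least one additional risk factor for CVD, but no established CVD". Diabetic patients who have established CVD count in Category 1. The planned mix is "Approximately 70% of randomized patients will be in the CV Risk Category 1 and approximately 30" per cent in Category 2, and enrolment in a category stops when its target is reached.
- **Subgroup model (Section 12.2.4.5).** Each subgroup variable gets a Cox model with treatment, the stratification factors, the subgroup and one treatment-by-subgroup interaction. On reporting, the section says: "P-values for testing the interaction terms will be provided". CV risk category and "the presence/absence of diabetes at baseline" are separate subgroup variables. The section is titled exploratory, makes no multiplicity adjustment, and leaves the complete subgroup list to the SAP.
- **Tertiary endpoint (Section 9.2.3).** The list includes "Primary endpoint in subset of patients with diabetes mellitus".

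**The concern.** The cell for patients with neither diabetes nor established CVD is empty by design. The diabetes contrast therefore sets patients who all have established CVD against a group holding the whole primary-prevention stratum. This is built into eligibility and is more than ordinary correlation between two subgroup variables.

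In the diabetes model, CV risk category can enter only as a main effect. That adjusts the baseline hazard and leaves the treatment effect unadjusted. If the drug works differently in the two categories, the difference passes into the diabetes interaction. The trial could then report a weaker effect in diabetic patients when the weaker effect belongs to patients without established CVD. It could also miss a real diabetes difference that Category 2 cancels out.

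One ambiguity adds to this. The section drops stratification factors for subgroup variables related to them. If diabetes counts as related, even the main effect of CV risk category is left out.

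**Working it through.** **The plan's own figure.** With HR 0.85, two-sided alpha 0.0476, 90% power and 1:1 allocation, the Schoenfeld formula gives 4 × (1.981 + 1.282)² / (ln 0.85)² = 1612 events, as Section 12.3 states. The plan gives no power for the diabetes interaction.

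**Inputs.** From the documents: a 70/30 mix, 1612 events, 1:1 allocation and a two-sided 5% level. Assumed, because the documents do not give them:
- *d*, the diabetic share of Category 1: 0.2 to 0.8
- *r*, the Category 2 hazard relative to Category 1: 0.5 to 1.0
- the hazard ratio in each cell.

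**Make-up of the diabetic subgroup.** The Category 2 share is 0.3 / (0.3 + 0.7*d*): 68% at *d* = 0.2, 46% at 0.5 and 35% at 0.8. It exceeds half only when *d* is below 0.3/0.7 = 43%. The one prevalence figure to hand is ANCHOR (Section 1.3), with 514/702 = 73.2% diabetic. By analogy only, that implies *d* = (0.732 − 0.3)/0.7 = 0.62 and a Category 2 share of 0.3/0.732 = 41%.

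**Formulas.** The 1612 events are split over three cells in proportion to patient share × relative hazard × (1 + HR)/2. The log HR in diabetics is the event-weighted mean of its two cells. The interaction SE is √(4/E_diabetic + 4/E_non-diabetic), with a Wald test at 1.96.

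**Worked case: HR 0.80 in Category 1 and 1.00 in Category 2, no diabetes effect, *d* = 0.5, *r* = 0.7.**
- Weights are 0.35 × 0.9 = 0.315, 0.315, and 0.3 × 0.7 = 0.21, giving 604.5, 604.5 and 403 events.
- Log HR in diabetics = 0.6 × ln 0.80 = −0.134, so the HR is 0.875 against 0.80 in non-diabetics, a ratio of 1.09.
- SE = √(4/604.5 + 4/1007.5) = 0.103 and z = 0.0893/0.103 = 0.87.
- Rejection probability is 14%.

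The same calculation over the range:

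| *d* | Category 2 share of diabetics | Ratio of HRs (*r* 0.5–1.0) | Planned test rejects |
|---|---|---|---|
| 0.2 | 68% | 1.13–1.17 | 21–35% |
| 0.3 | 59% | 1.10–1.15 | 17–28% |
| 0.5 | 46% | 1.07–1.11 | 11–18% |
| 0.62 | 41% | 1.06–1.10 | 9–14% |
| 0.8 | 35% | 1.05–1.09 | 7–9% |

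Within Category 1 the ratio is 1.00 and rejection is 5% throughout. With the same HR in both categories, the planned test also rejects 5%. A small Cox simulation (60 replicates, about 1380 events; HR 0.75 and 1.00, *d* = 0.43, *r* = 0.7) rejected 25% with the planned model and 7% with a treatment-by-category term added.

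**Masking.** Take HR 0.90 (Category 1 without diabetes), 0.70 (Category 1 with diabetes) and 1.00 (Category 2). Over the same ranges the planned test rejects 5 to 29% of the time, against 36 to 62% within Category 1.

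**Cost in power if only diabetes matters** (0.90 without diabetes, 0.70 with, in either category). At *d* = 0.5 and *r* = 0.7 the cells hold 663, 593 and 356 events.
- Planned: SE = √(4/663 + 4/949) = 0.101, power 70%.
- Within Category 1: SE = √(4/663 + 4/593) = 0.113, power 60%.
- Over *d* 0.3–0.5 and *r* 0.5–0.7: about 69–71% planned and 52–63% within Category 1.

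**The case against.** The strongest reply is that nothing is wrong with the test. Section 12.2.4.5 sets out to assess consistency across subgroups; it does not state a null conditional on CV risk category. In the worked case the HR among enrolled diabetics really is 0.875 against 0.80, so rejecting is correct for those groups. This stands. A reader might infer that the planned test has an inflated type I error, and the documents do not support that. What fails is the attribution to diabetes.

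A reader might also infer that the diabetic subgroup is largely primary prevention. The documents do not give the diabetic share of Category 1, and the ANCHOR analogy points to a minority, about 41%.

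The assumed gap between categories is also uncertain. Section 1.5 describes omega-3 intake studies "with a stronger effect in secondary prevention". It also cites the ethyl-EPA plus statin trial, with reductions of 18% without and 19% with coronary disease, and a 53% reduction in a higher-risk primary-prevention subgroup. Neither size nor direction is settled, and the masking case is purely illustrative.

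CV risk category has its own interaction test. With HR 0.80 and 1.00 and *r* of 0.5 to 0.7, Categories 1 and 2 hold 1302 and 310, or 1209 and 403, events. The SE is 0.126 or 0.115, and that test rejects about 42 to 49% of the time, so readers would often see the more direct signal. But its contrast is mixed in the other direction, since Category 2 is all diabetic. Neither row gives the HR for diabetic patients with established CVD.

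The SAP might already contain a Category 1 breakdown. That cannot be ruled out; the protocol text specifies none.

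**Conclusion.** The point holds as a limit on interpretation. The planned interaction compares the subgroups as enrolled and is valid for that. It cannot say whether diabetes itself modifies the effect. Under the assumed HRs of 0.80 and 1.00, a diabetes difference would be declared about 7 to 35% of the time with no diabetes effect. By analogy with ANCHOR the figure is about 9 to 14%. The distortion shrinks as more of Category 1 is diabetic and vanishes if the effect does not differ by category.

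A reader might go further and doubt the trial's result in diabetic patients. The documents do not support that: the tertiary endpoint in the diabetic subset is a randomized comparison within that subset, and the interaction model does not touch it. No primary or key secondary conclusion depends on this test. It is a cheap improvement to an exploratory analysis.

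**What to change.** Keep the planned diabetes row. In Section 12.2.4.5 and the SAP, before unblinding:

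1. Add the treatment-by-diabetes test within CV Risk Category 1, the only stratum that holds both kinds of patient. Adding a treatment-by-CV-risk-category term to the diabetes model does the same job, because Category 2 then no longer informs the diabetes interaction.
2. Show hazard ratios with confidence intervals for three cells: Category 1 without diabetes, Category 1 with diabetes, and Category 2.
3. State that any claim that diabetes itself modifies the effect rests on the within-Category 1 result.
4. Say whether diabetes counts as a variable related to the stratification factors.

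The cost is one extra test and a few table entries from data already collected. The added test has less power because only Category 1 informs it, which is the reason to add it beside the planned row and not to replace that row.
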